5.1.7.2 ADRs Requiring Treatment Discontinuation or Modifications

The following ADRs require permanent treatment discontinuation of avelumab:

Any Grade 4 ADRs require treatment discontinuation except for single laboratory values out of normal range that are unlikely related to trial treatment as assessed by the investigator, do not have any clinical correlate, and resolve within 7 days with adequate medical management.

Any Grade 3 ADRs require treatment discontinuation except for any of the following:

- Transient (≤ 6 hours) Grade 3 flu-like symptoms or fever, which is controlled with medical management.
- Transient (≤ 24 hours) Grade 3 fatigue, local reactions, headache, nausea, emesis that resolves to \leq Grade 1.
- Single laboratory values out of normal range (excluding \geq Grade 3 liver function test increase) that are unlikely related to trial treatment according to the investigator, do not have any clinical correlate, and resolve to \leq Grade 1 within 7 days with adequate medical management.
- Tumor flare phenomenon defined as local pain, irritation, or rash localized at sites of known or suspected tumor.
- Any Grade ≥ 3 drug-related amylase or lipase abnormality that is not associated with symptoms or clinical manifestations of pancreatitis does not require dose delay. The Study Medical Monitor should be consulted for such Grade ≥ 3 amylase or lipase abnormalities.
- Increases in ECOG performance status ≥ 3 , which do not resolve to ≤ 2 by cycle Day 14 of the following cycle (infusions should not be given on the following cycle, if the ECOG performance status is ≥ 3 on the day of study drug administration).

Any Grade 2 ADR should be managed as follows:

- Infusion should not be given in case of ongoing Grade 2 ADR on the day of trial treatment administration.
- Treatment can be resumed according to original schedule once ADR resolved to Grade ≤ 1 . Up to 2 subsequent study drug doses may be omitted. If more than two doses are skipped, treatment may be resumed after consultation with study Medical Monitor.
- Infusion-related reactions, hypersensitivity reactions (Grades 1 to 4), tumor lysis syndrome, and irAEs should be handled according to the guidelines provided in Sections [6.5.4.1](#), [6.5.4.2](#), [6.5.4.3](#), [6.5.4.4](#), respectively.

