5.5.2 Withdrawal From the Investigational Medicinal Product

The subject must be withdrawn in the event of any of the following:

- Occurrence of an exclusion criterion, which is clinically relevant and affects the subject's safety, if discontinuation is considered necessary by the investigator and/or Sponsor.
- Therapeutic failure requiring urgent additional drug (if applicable).
- Occurrence of any Grade ≥ 3 ADRs as defined in Section 5.1.7.
- Occurrence of AEs, resulting in the discontinuation of trial drug being desired or considered necessary by the investigator and/or the subject (if applicable).
- Occurrence of pregnancy (if applicable).
- Use of a non-permitted concomitant drug, as defined in Section 6.5.2, where the predefined consequence is withdrawal from the IMP (the Sponsor may be contacted to discuss whether the trial treatment must be discontinued).
- Non-compliance (see Section 6.9).

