4. Previous malignant disease other than the target malignancy to be investigated in this trial within the last 5 years with the exception of basal or squamous cell carcinoma of the skin or cervical carcinoma in situ	Eligibility and Entry Criteria	Subject met exclusion criterion 4 (previous malignant disease other than the target malignancy to be investigated in this trial within the last 5 years).	PDEV09	Section 5.3.2		Medical review required
12. Pregnancy or lactation period.	Eligibility and Entry Criteria	Subject met exclusion criterion 12 (pregnancy or lactation period).	PDEV10	Section 5.3.2	PREG.PRRLTCD	Medical review required.

	Category of Protocol Deviation	Description of Protocol Deviation	Deviation Code	Protocol Section	Variable [dataset]	Proposed check / comment
Non-permitted concomitant medication during the study	Concomitant Medication Criteria	Subject took prohibited medication during the study.	PDEV11	Section 6.5.2	CMED.CMTERM	Medical review required
Subjects that developed withdrawal criteria whilst on the study but were not withdrawn;	Other Criteria	Subject became pregnant, but continued on the study.	PDEV12	Section 5.5.2	LB.LBORRES, BTESTCD; DS.DSSTDTC, DSSCATE;	Medical review required.
Subjects that developed withdrawal criteria whilst on the study but were not withdrawn;	Other Criteria	Subjects had ECOG>=3, did not resolved to <=2 by day 14 of next cycle, and continued on the study.	PDEV13	Section 5.1.7.2 and 5.5.2	XP.XPORRES, XPDY; DS.DSSTDTC, DSSCATE;	Medical review required.
Subjects that developed withdrawal criteria whilst on the study but were not withdrawn;	Other Criteria	Subject developed grade 4 AE, but continued on the study.	PDEV14	Section 5.1.7.2 and 5.5.2	ADAE.ATOXGRN, TRTEMFL, AREL; SDTM.AE.AEACNOT H; SUPPAE.QVAL, QNAM	List if TOXGRN=4 and AREL='Related' and TRTEMFL='Y' and (SUPPAE.QVAL^='Drug Withdrawn' where QNAM in (ACNMSB, ACNMSB3) and SDTM.AEACNOTH^='LED TO STUDY TERMINATION')
Subjects that developed withdrawal criteria whilst on the study but were not withdrawn;	Other Criteria	Subject developed grade 3 AE, but continued on the study.	PDEV15	Section 5.1.7.2 and 5.5.2	ADAE.ASEVN, TRTEMFL, AEDECOD, AEDUR. DS.DSSTDTC, DSSCATE;	Medical review required.

	Category of Protocol Deviation	Description of Protocol Deviation	Deviation Code	Protocol Section	Variable [dataset]	Proposed check / comment

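### Protocol 5.1.7.2 lists non-resolving ECOG ≥3 as an exception to stopping avelumab, while expansion SAP PDEV13 counts it as a withdrawal criterion

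*Protocol*

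**What the plan says.** Protocol 5.1.7.2 opens with "The following ADRs require permanent treatment discontinuation of avelumab". A paragraph on Grade 4 reactions follows, and then the Grade 3 rule: "Any Grade 3 ADRs require treatment discontinuation except for any of the following". Six bullets stand under that rule. The first five cover brief flu-like symptoms or fever; brief fatigue, local reactions, headache, nausea or emesis; isolated laboratory values that settle within 7 days; flare at tumor sites; and amylase or lipase changes without pancreatitis. The sixth is "Increases in ECOG performance status ≥ 3 , which do not resolve to ≤ 2 by cycle Day 14 of the following cycle". Its bracket adds that "infusions should not be given on the following cycle, if the ECOG performance status is" 3 or worse on the dosing day.

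Protocol 5.5.2 lists the reasons for withdrawal from the drug, and none names ECOG. The nearest entries are "Occurrence of any Grade ≥ 3 ADRs as defined in Section 5.1.7" and the discretionary "Occurrence of AEs, resulting in the discontinuation of trial drug being desired or considered necessary by the investigator and/or the subject".

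Expansion SAP Appendix I describes PDEV13 as "Subjects had ECOG>=3, did not resolved to <=2 by day 14 of next cycle, and continued on the study" and files it under "Subjects that developed withdrawal criteria whilst on the study but were not withdrawn". The entry cites protocol 5.1.7.2 and 5.5.2 and is marked for medical review.

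On the minor point, Table 6.2 in protocol 6.5.4.4 offers a choice between delaying and stopping for Grade 3–4 rash, and allows a restart once the rash has improved to Grade 1.

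**The concern.** The two documents point in opposite directions for the same event. Read literally, the protocol exempts a subject whose ECOG status stays at ≥3 from mandatory discontinuation. The SAP counts the same subject, if kept on, as an important deviation, and it cites the protocol section that grants the exemption.

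What is at stake is a time limit within a safety-stopping rule. If the item is a trigger, a subject has until Day 14 of the following cycle to recover. If it is an exception, there is no limit and treatment may restart whenever ECOG returns to ≤2. A site following the printed protocol could therefore produce a deviation that the protocol does not recognise.

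**Working it through.** This is mainly a comparison of texts; the arithmetic is limited to steps 5 and 7.

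1. **Position.** In the supplied text the Grade 4 and Grade 3 lines are plain paragraphs. Every bullet after the Grade 3 line, including the ECOG one, is at the same level. By position, the ECOG item is an exception.

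2. **Meaning.** The other five items describe events that are brief, resolving, local or without clinical signs. Only the ECOG item is conditioned on failure to resolve. It makes sense under the opening stem and not under the exceptions.

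3. **Tracing PDEV13.** It cites two protocol sections. Section 5.1.7.2, as printed, exempts the event. Section 5.5.2 has no ECOG line, and its Grade ≥3 entry refers back to 5.1.7. As printed, neither section supports PDEV13.

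4. **Where the readings lead to different treatment.**
   - ECOG returns to ≤2 by the limit: dosing may continue under both readings.
   - ECOG stays ≥3: no infusion is given under either reading.
   - ECOG returns to ≤2 after the limit: treatment may restart as printed, whereas under PDEV13 the subject should already have been withdrawn.

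   Only the third case differs in drug given.

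5. **Length of the limit.** The cycle is 14 days (protocol 6.2). Counted from Day 1 of the current cycle, Day 14 of the following cycle is day 14 + 14 = 28. If ECOG ≥3 is recorded on Day 1, the time allowed is 28 − 1 = 27 days. If it is recorded on Day 14, it is 28 − 14 = 14 days. ECOG is scheduled every 2 weeks before dosing (protocol 7.1.2.2), so 27 days is the usual case and 14 days would need an unscheduled assessment. As printed, there is no limit.

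6. **Other rules that could stop the subject.** Protocol 7.3 allows treatment beyond RECIST progression only if performance status has not worsened. It also requires an immediate stop for intolerance, or for therapeutic failure with urgent need of another drug or clinically significant deterioration. Related Grade 3 fatigue lasting more than 24 hours is not excepted in 5.1.7.2. Section 5.5.2 leaves room for discretion. These rules narrow the gap, but none sets a fixed time for ECOG recovery.

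7. **Grade 3–4 rash.** The exceptions in 5.1.7.2 do not cover rash apart from tumor-site flare, whereas Table 6.2 allows a restart. The programmed PDEV14 check flags a related Grade 4 event without drug withdrawal and makes no allowance for immune-related events. PDEV15 (Grade 3) goes through medical review. As to size, protocol Table 3.2 lists Grade ≥3 terms down to 7/480 = 1.46% at the 5 November 2014 cut-off and contains no rash term. Any single rash preferred term was therefore at most 6/480 = 1.25%.

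**The case against.** The strongest objection is that this is damage from reading the PDF. The supplied text does lose list structure elsewhere: in protocol 5.3.1 several inclusion criteria appear as plain bullets, although the synopsis prints the same criteria with numbers. In 5.1.7.2 itself, the last bullet under the Grade 2 heading covers hypersensitivity reactions of Grades 1 to 4, so it cannot belong to a Grade 2 list. A lost indent would explain both stray bullets, and if that is the cause the plan contains no error. This lowers confidence but does not settle the matter, because the text as supplied places the ECOG item squarely among the exceptions. Checking the original page will decide it.

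It is also fair to say that the intent is plain. The item reads as a trigger, PDEV13 uses it as one, and a medical reviewer rather than a program decides each case. That stands, and it is why the effect is small. It does not make the printed rule correct for a site that follows it.

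On rash, 5.1.7.2 sends immune-related events to 6.5.4.4, which in turn directs that they be treated according to Table 6.2. The specific rule can therefore be read as governing. That answers most of the point. What remains is that the cross-reference stands under the Grade 2 heading and that PDEV14 does not reflect it.

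Finally, this is Amendment 18, dated August 2018, with last subject out planned for Q2 2019. Few treatment decisions may still be affected, though the classification of deviations is.

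**Conclusion.** The inconsistency is present in the supplied text and should be corrected if the original layout confirms it. Confidence is moderate, because the point turns on the level of one bullet. The comparison uses the expansion SAP only.

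The effect is small. It concerns drug given to subjects who recover to ≤2 after the limit, and how such subjects are classed. The documents give no count, and I offer none. The ECOG shift table in expansion SAP 17.5 will show how many reached ≥3 on treatment, which is an upper limit. I have read the bracketed hold as applying at every dosing visit with ECOG ≥3, although its words name only the following cycle.

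Three stronger readings are tempting and are not supported:

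- A reader might infer that the protocol permits infusions at ECOG ≥3. The bracket in the same bullet forbids them.
- A reader might infer that the efficacy results are compromised. Expansion SAP 12.2.2 only tabulates and lists important deviations, and the full analysis set is all treated subjects. The primary endpoint, power and alpha are untouched.
- A reader might infer that Table 6.2 contradicts 5.1.7.2 for immune-related events in general. For Grade 3–4 diarrhea or colitis, pneumonitis and liver test elevations, and for immune-mediated myocarditis, both say stop. The endocrine rows that allow delay or a restart carry no grade, so they conflict only if the event is Grade 3–4. Real tension is left only for Grade 3–4 rash.

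**What to change.** First check the bullet level in the original protocol file. If the ECOG item already stands outside the exception list there, no change is needed.

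Otherwise, move it to its own line under the opening stem of 5.1.7.2, so that ECOG ≥3 not resolved to ≤2 by Day 14 of the following cycle requires permanent discontinuation. Keep the hold on dosing at ECOG ≥3. PDEV13 can then stay as it is. The cost is one moved bullet, with no change to data collection, sample size or analysis.

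For the minor point, add a sentence stating whether Table 6.2 or the Grade 3/4 rule in 5.1.7.2 governs Grade 3–4 rash. If Table 6.2 governs, adjust the PDEV14 check and the PDEV15 review criteria to match. The clinical choice belongs to the sponsor's clinical team.

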5.1.8 Analysis Cut-Off Dates

After the end of the dose escalation part of the trial, a full analysis for safety and PK / PD data will be made and a full clinical trial report will be prepared. The cut-off date will be the time point when all subjects complete at least their first three 2-week treatment cycle, i.e., 6 weeks after the last subject of the escalation part has received its first administration of avelumab.

The primary data cut-off for the once weekly 10 mg/kg cohort is 4 weeks after the last evaluable subject in this cohort started treatment.

The primary data cut-off for the expansion cohorts is 6 months after the last subject started treatment.

An interim analysis of response will be conducted for each of the primary expansion cohorts after the first 75 subjects have reached the time point of their second post-baseline tumor assessment scheduled in Week 13, i.e., 13 weeks after start of treatment of the 75th subject. In addition, for the ovarian cancer secondary expansion cohort, an interim analysis of response will be performed for internal planning purposes 13 weeks after the start of treatment of the 75th subject.

In the first-line NSCLC primary expansion cohort, an interim analysis of response will be conducted 13 weeks after start of treatment of the 30th subject.

In the efficacy expansion cohorts, interim analyses for efficacy are planned 13 weeks after the start of treatment of the 30th subject in all cohorts, 13 weeks after start of treatment of the 60th subject in the ovarian cohort, and 13 weeks after start of treatment of the 90th subject in the gastric / GEJ and HNSCC cohorts. No futility rule is foreseen because the clinical activity of anti-PD-1 / anti-PD-L1 agents in these tumor types is established, and the patient populations are characterized by a high unmet medical need. If efficacy criteria are met at the interim analysis, enrollment will continue to the planned full number of subjects in order to collect further data on the primary and secondary endpoints, especially on the association between PD-L1 expression and efficacy endpoints.

An interim analysis will be conducted at 6 months after the last subject's first dose of study treatment for the 109 subjects enrolled in the urothelial carcinoma efficacy expansion cohort prior to Protocol Amendment 13.

In addition, in the NSCLC post platinum doublet cohort only, 2 additional interim analyses of efficacy will be conducted, 13 weeks after the start of treatment of the 60th and the last subject, respectively.

For each primary or secondary expansion cohort, an additional interim analysis may be conducted 13 weeks after the start of treatment of the last subject in that cohort.

Interim analyses for 6 of the 8 secondary cohorts are planned as described in Section 8.6.

Final data cut-off will be 1 year after the last dose of avelumab has been administered.

5.2 Discussion of Trial Design

This is a Phase I, open-label, dose-escalation trial with a planned consecutive expansion part in selected tumor indications. An open-label, unblinded design is appropriate for a dose-escalation trial with consecutive expansion cohorts in cancer subjects.

In this trial, the assessment of the safety and tolerability of the IMP with the determination of the MTD (in the dose escalation part only) is set to be the primary objective. The determination of the MTD is one of the first major steps in the development of a compound entering early clinical development because it is expected to use a dose close to the highest tolerable dose in future clinical development in order to achieve the best efficacy to risk ratio for subjects. The MTD will be determined using a standard “3 + 3 subjects” dose escalation design based on DLT assessments, which is commonly used in first-in-man oncology trials (67). The aim of this design is to maximize the protection to subjects and reduce the chances of more subjects to be exposed to possible drug toxicities. However, at the end of the dose-escalation part, it is intended to fill cohorts as described in Section 5.1.1 to identify a reasonable dose and schedule for the expansion part. All these assessments will be correlated to PK / PD parameters to identify the most meaningful dose for expansion cohorts in selected tumor indications.

The enrichment of dose-escalation cohorts below the MTD is reasonable for immunotherapeutic anticancer compounds (which is in contrast to most chemotherapies, that are typically given at the MTD), as the optimal biological effects are often not exclusively observed at the MTD level but already significantly below (6,68).

A reasonably safe starting dose of 1.0 mg/kg has been identified both via a NOAEL based or a PAD driven approach taking also into account the available information on clinical experience with BMS-936559, an anti-PD-L1 monoclonal antibody, which can be considered as clinical surrogate and gives an estimate of the irAEs to be expected at various dose levels (5). Initial dose setting follows the principle that the start dose should be pharmacologically active but also reasonably safe to use. This initial dose estimation algorithm is proposed in Guideline ICH S9 (8) and applicable for an end-stage cancer population.

In addition to determining the MTD, the study will serve to explore biologic and clinical parameters after exposure to avelumab. Due to a limited understanding of the interaction of the immune system and tumors in cancer subjects, there can be no certainty that the doses to be

examined will be associated with relevant anti-tumor activity. The selection of the dose to be used for further clinical evaluation will be based on the best current scientific knowledge.

The target population for the dose-escalation part comprises subjects with metastatic or locally advanced solid tumors. Based on the literature, tumor indications with an over-expression of PD-L1 are selected. These include NSCLC, gastric / GEJ cancer, MBC, CRC, CRPC, melanoma, ovarian cancer, HNSCC, and RCC. In order to obtain a trend of biological / clinical activity in these and in other relevant indications (ACC, mesothelioma, and urothelial carcinoma) and to collect further safety data, a treatment expansion at a meaningful dose level and regimen to be identified during the dose-escalation part to ensure further development in selected settings is justified. Furthermore, data from the expansion cohorts will allow to explore whether the expression of membrane PD-L1 is associated with clinical response to PD-L1 blockade and whether PD-L1 expression might serve as a marker for patient selection in the future development program of avelumab.

The tests and analyses to examine the biologic effects of the avelumab regimen will be the assessment of general markers of immune activation known to show typical changes after treatment with therapies blocking immune checkpoints. These details are specified in Section 7.6.

5.2.1 Inclusion of Special Populations

Not applicable.

5.3 Selection of Trial Population

5.3.1 Inclusion Criteria

For inclusion in the trial, all of the following inclusion criteria must be fulfilled:

Inclusion criteria for dose escalation, including the 10 mg/kg once weekly cohort:

1. Signed written informed consent.
2. Male or female subjects aged ≥ 18 years.
3. Histologically or cytologically proven metastatic or locally advanced solid tumors, for which no standard therapy exists or standard therapy has failed. Availability of tumor archival material or fresh biopsies is optional for subjects in dose escalation.
4. ECOG performance status of 0 to 1 at trial entry and an estimated life expectancy of at least 3 months.
5. Disease must be measurable with at least 1 unidimensional measurable lesion by RECIST 1.1, except for subjects with metastatic CRPC or MBC who may be enrolled with objective evidence of disease without a measureable lesion.
6. Adequate hematological function defined by white blood cell (WBC) count $\geq 3 \times 10^9/L$ with absolute neutrophil count (ANC) $\geq 1.5 \times 10^9/L$, lymphocyte count $\geq 0.5 \times 10^9/L$, platelet count $\geq 100 \times 10^9/L$, and hemoglobin ≥ 9 g/dL (may have been transfused). For subjects with

gastric cancer only, the acceptable parameters for WBC, ANC, and lymphocytes are as follows: $WBC \geq 2 \times 10^9/L$, $ANC \geq 1.0 \times 10^9/L$, and lymphocyte count $\geq 0.5 \times 10^9/L$.

- Adequate hepatic function defined by a total bilirubin level $\leq 1.5 \times$ the upper limit of normal range (ULN), an AST level $\leq 2.5 \times$ ULN, and an ALT level $\leq 2.5 \times$ ULN or, for subjects with documented metastatic disease to the liver, AST and ALT levels $\leq 5 \times$ ULN.
- Adequate renal function defined by an estimated creatinine clearance > 50 mL/min according to the Cockcroft-Gault formula.
- Highly** effective contraception (that is, methods with a failure rate of less than 1% per year) for both male and female subjects if the risk of conception exists (Note: The effects of the study treatment on the developing human fetus are unknown; thus, women of childbearing potential and men must agree to use highly effective contraception, defined in [Appendix III](#) or as stipulated in national or local guidelines. **Highly** effective contraception must be used 28 days prior to first study treatment administration, for the duration of study treatment, and at least for 60 days after stopping study treatment. Should a woman become pregnant or suspect she is pregnant while she or her partner is participating in this study, the treating physician should be informed immediately.)

Inclusion criteria for expansion phase:

- Signed written informed consent.
- Male or female subjects aged ≥ 18 years.
- Subjects must have relapsed, refractory, or progressive disease following last line of treatment (with the exception of the NSCLC first-line and gastric and GEJ cancer primary cohorts, which do not require progression). Availability of tumor archival material or fresh biopsies (excluding bone biopsies) is mandatory for eligibility in the expansion cohorts. For subjects in the MBC cohort, the biopsy or surgical specimen must have been collected within 90 days prior to the first IMP administration. Specifically, the following will be required:

Primary expansion cohorts

- NSCLC post platinum doublet:** Histologically or cytologically confirmed stage IIIB or stage IV NSCLC that has progressed after 1 line of platinum-containing doublet chemotherapy. Subjects should have received only 1 line of platinum-containing treatment for metastatic disease (i.e., adjuvant treatment with a platinum-containing regimen is not sufficient for eligibility because not received in the context of a metastatic disease). Subjects in the NSCLC cohort will only be enrolled in the USA.
- NSCLC first line:** Stage IV (per 7th International Association for the Study of Lung Cancer [IASLC] classification) or recurrent NSCLC that is histologically proven. Subjects must not have received treatment for their metastatic or recurrent disease. No activating EGFR mutation nor ALK translocation / re-arrangement (non-squamous cell histologies require testing if status is unknown).
- Gastric and GEJ cancer, first-line maintenance or second-line:** Histologically confirmed, unresectable locally advanced or metastatic adenocarcinoma of the gastric

and GEJ, treated with first-line chemotherapy combination in metastatic setting with or without disease progression. Subjects should have received no more than 1 line of treatment for metastatic disease. Subjects should not have been treated with trastuzumab (but can be Human Epidermal growth factor Receptor 2 [HER2] positive). Subjects who received any platinum containing doublet or triplet as a neoadjuvant chemotherapy strategy, but are not ultimately candidates for surgery will also be eligible. In addition, subjects with gastric cancer can enter in the study if their WBC is $\geq 2 \times 10^9/L$ with ANC $\geq 1.0 \times 10^9/L$ and lymphocyte count $\geq 0.5 \times 10^9/L$.

- **MBC:** Subjects must have histologically confirmed locally advanced or MBC and have tumor that is refractory to or progressive after standard of care therapy. Subjects must have received no more than 3 prior lines of cytotoxic therapy for metastatic disease. Subjects must have received a taxane and an anthracycline, unless contra-indicated.

Secondary expansion cohorts

- **CRC:** Histologically or cytologically confirmed recurrent or refractory metastatic CRC (according to AJCC/UICC TNM Staging System seventh edition) after failure of prior therapy containing oxaliplatin/fluoropyrimidine and/or irinotecan/fluoropyrimidine and, if eligible, cetuximab (Erbix®) and bevacizumab (Avastin®). These subjects will be enrolled in sites located in the USA only.
- **CRPC:** Histologically or cytologically confirmed asymptomatic metastatic CRPC or minimally symptomatic (according to AJCC/UICC TNM Staging System seventh edition) with objective evidence of disease (non measurable or measurable lesion) with stable, ongoing adequate testosterone suppression proven by castrate levels of testosterone (≤ 50 ng/dL), except for subjects with prior orchiectomy. Minimally symptomatic is defined as patients who do not require consistent treatment with opiates over the last month (less than 7 days of opiates in the last 28 days, and no opiates administered 3 days in a row), for the treatment of their prostate cancer. Additional androgen blockade or treatment with an anti-androgen receptor is acceptable. These subjects will be enrolled in sites located in the USA only.
- **Melanoma:** Histologically or cytologically confirmed stage IIIc or IV unresectable melanoma (according to AJCC/UICC TNM Staging System seventh edition) after failure of at least 1 prior standard therapy for metastatic disease. All subjects with metastatic melanoma will be required to undergo screening with a MRI or CT scan (either, with contrast preferred) to rule out brain metastases, unless imaging has previously been performed within 28 days prior to screening.
- **Ovarian cancer:** Histologically or cytologically confirmed recurrent or refractory (progression within 6 months of platinum-based therapy or progression after subsequent therapy in previously relapsed subjects), stage III-IV epithelial ovarian, fallopian tube or peritoneal cancer subjects (according to AJCC/UICC TNM and International Federation of Gynecology and Obstetrics (FIGO) Staging System seventh edition) who have progressed following adjuvant therapy or therapy for metastatic disease.

- **ACC:** Histologically or cytologically confirmed metastatic ACC. Subjects must have previously received at least 1 line of systemic therapy for metastatic disease, of which at least 1 must be platinum-based. Subjects receiving mitotane may continue to receive mitotane at enrolment and on study.
- **Mesothelioma:** Histologically or cytologically confirmed mesothelioma (pleural or peritoneal) with unresectable disease. Subjects must have received and progressed after either a platinum-pemetrexed containing regimen or a platinum-containing regimen followed by pemetrexed (or vice versa) after disease progression. Subjects must present with at least 1 measurable lesion that has not been irradiated.
- **Urothelial carcinoma:** Histologically or cytologically documented locally advanced or metastatic transitional cell carcinoma of the urothelium (including renal pelvis, ureters, urinary bladder, urethra). A tumor sample (1 tumor block or at least 7 unstained slides) must be available. Subjects can be either: ineligible for cisplatin-based chemotherapy or have progressed after treatment with at least 1 platinum-containing regimen (e.g., platinum plus another agent such as gemcitabine, methotrexate, vinblastine, doxorubicin, etc.) for inoperable locally advanced or metastatic urothelial carcinoma or disease recurrence. Ineligibility to treatment with a platinum salt is defined by the existing of any (at least 1) of impaired renal function, a hearing loss of 25 decibels at 2 contiguous frequencies, or Grade ≥ 2 peripheral neuropathy. Subjects may have received any number of prior systemic therapies for metastatic disease.
- **Renal cell carcinoma, second-line with first-line expansion:** Histologically or cytologically documented RCC with a component of clear cell subtype, with metastasis. A tumor sample (1 tumor block or at least 7 unstained slides) must be available. Eligible subjects must have measurable disease. Subjects must have failed 1 prior systemic first-line regimen for metastatic RCC (except for subjects enrolled in first-line expansion).

Efficacy expansion cohorts:

- **Gastric and GEJ cancer, third line:** Histologically confirmed, unresectable locally advanced or metastatic adenocarcinoma of the gastric and GEJ, treated with both a first-line chemotherapy combination and followed by ramucirumab (alone or in combination). Subjects must have progressed during or after ramucirumab therapy. Subjects with gastric cancer can enter into the study if their WBC is $\geq 2 \times 10^9/L$ with ANC $\geq 1.0 \times 10^9/L$ and lymphocyte count $\geq 0.5 \times 10^9/L$.
- **Ovarian cancer, platinum refractory and prior liposomal doxorubicin:** Histologically or cytologically confirmed, platinum-refractory (progression within 6 months of platinum-based therapy), Stage III-IV epithelial ovarian, fallopian tube, or peritoneal cancer subjects (according to AJCC/UICC TNM and FIGO Staging System, 7th edition). Subjects must have received at least 1 line of prior platinum-based chemotherapy regimen, as well as prior liposomal doxorubicin (monotherapy or combination), in order to be considered eligible for this study. Subjects may have received any additional number of prior systemic therapies for metastatic disease.

- **Urothelial carcinoma, platinum ineligible or progressed after at least 1 line of platinum-based therapy:** Histologically or cytologically documented locally advanced or metastatic transitional cell carcinoma of the urothelium (including renal pelvis, ureters, urinary bladder, urethra). A tumor sample (1 tumor block or at least 7 unstained slides) must be available. Subjects can be either: ineligible for cisplatin based chemotherapy or have progressed after treatment with at least 1 platinum-containing regimen (e.g., platinum plus another agent such as gemcitabine, methotrexate, vinblastine, doxorubicin, etc.) for inoperable locally advanced or metastatic urothelial carcinoma or disease recurrence. Ineligibility to treatment with a platinum salt is defined by the existing of any (at least 1) of impaired renal function, a hearing loss of 25 decibels at 2 contiguous frequencies, or Grade ≥ 2 peripheral neuropathy. Subjects may have received any number of prior systemic therapies for metastatic disease.
 - **Head and neck, platinum ineligible or progressed after at least 1 line of platinum-based therapy:** Histologically or cytologically documented recurrent or metastatic HNSCC of the oral cavity, oropharynx, hypopharynx, or larynx. Subjects must have experienced tumor progression or recurrence within 6 months of the last dose of any number of platinum-based chemotherapy regimens given in the adjuvant, primary, recurrent, or metastatic setting. Ineligibility to treatment with a platinum salt is defined by the existing of any (at least 1) of impaired renal function, a hearing loss of 25 decibels at 2 contiguous frequencies, or Grade ≥ 2 peripheral neuropathy. A tumor sample (1 tumor block or at least 7 unstained slides) must be available. Subjects may have received any number of prior systemic therapies for metastatic disease. Except for subjects who are platinum ineligible, subjects must have received at least 1 line of platinum-based chemotherapy.
4. ECOG performance status of 0 to 1 at trial entry and an estimated life expectancy of at least 3 months.
 5. Disease must be measurable with at least 1 unidimensional measurable lesion by RECIST 1.1, except for subjects with metastatic CRPC who may be enrolled with objective evidence of disease without a measureable lesion.
 6. Adequate hematological function defined by $WBC \geq 3 \times 10^9/L$ with $ANC \geq 1.5 \times 10^9/L$, lymphocyte count $\geq 0.5 \times 10^9/L$, platelet count $\geq 100 \times 10^9/L$, and hemoglobin ≥ 9 g/dL (may have been transfused). For subjects with gastric cancer only, the acceptable parameters for WBC, ANC, and lymphocytes are as follows: $WBC \geq 2 \times 10^9/L$, $ANC \geq 1.0 \times 10^9/L$, and lymphocyte count $\geq 0.5 \times 10^9/L$.
 7. Adequate hepatic function defined by a total bilirubin level $\leq 1.5 \times ULN$ and an AST level $\leq 2.5 \times ULN$ and an ALT level $\leq 2.5 \times ULN$ for all subjects.
 8. Adequate renal function defined by an estimated creatinine clearance > 30 mL/min according to the Cockcroft-Gault formula or measured 24-hour creatinine clearance (or local institutional standard method).
 9. **Highly** effective contraception (that is, methods with a failure rate of less than 1% per year) for both male and female subjects if the risk of conception exists (Note: The effects of the study treatment on the developing human fetus are unknown; thus, women of childbearing

potential and men must agree to use highly effective contraception, defined in [Appendix III](#) or as stipulated in national or local guidelines. **Highly** effective contraception must be used 28 days prior to first study treatment administration, for the duration of study treatment, and at least for 60 days after stopping study treatment. Should a woman become pregnant or suspect she is pregnant while she or her partner is participating in this study, the treating physician should be informed immediately.)

